The proposed study will be conducted in kindergartens in Hong Kong. The communal water supply in Hong Kong is fluoridated at a concentration of 0.5 ppm. Most child formula toothpastes available in Hong Kong contain fluoride at a concentration of 500–600 ppm. Generally healthy children aged between 3-4 years with no remarkable medical history will be invited to participate in this study. Children with at least one of the following criteria, deemed to be at moderate to high caries risk (American Academy of Paediatric Dentistry, 2013), will be included in this study:

Moderate risk	The child is a recent immigrant.
	The child has plaque on teeth.
High risk	The parent/ caregiver has low socioeconomic status.
	The child has >3 between meal sugar-containing snacks or beverages per day.
	The child is put to bed with a bottle containing natural or added sugar.
	The child has >1 decayed/missing/filled

	surfaces.
	The child has white spot lesions or enamel defects.
	The child has visible cavities or fillings.

They are thus qualified to receive fissure sealants and topical fluoride application regularly every 3 months (Lee, 2015; AAPD, 2013).

The following will be excluded from this study:

1. Children with the presence of caries of ICDAS code 3, 4, 5, or 6 on other primary teeth.
2. Children who had received professional fluoride application in the past 6 months.
3. Children with serious systemic disease or taking long term medication.
4. Children who are uncooperative or refuse the treatment.
5. Second primary molars that are (i) with caries in dentin indicated by ICDAS code 4, 5 or 6; (ii) partially erupted; (iii) with fillings and/or sealants; and (iv) hypoplastic or hypomineralized.

(ii) Methods

Sample size calculation

The primary outcome of this clinical trial is carious cavity development into dentin (ICDAS code 4,5 and 6) on occlusal surfaces of primary second molars. Sample size is calculated to be 256 children with a type I error of 0.05 and a power of 90%. This is based on the results of a previous study on primary molars (Honkala et al., 2015), where the real difference between fluoride varnish and sealant effect on occlusal caries reduction was 30%. Calculating with a 5% statistical significance level and a 90% power, a minimum of 102 children in each group will be required. To allow for loss of power due to drop-out, the initial sample size should be around 25%

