larger, i.e. 128 children are needed in each group at the beginning of the study. Thus, the total initial sample size will be 256 (128 x 2 groups).

Ethical approval

Ethical approval will be obtained from the Institutional Review Board of the University of Hong Kong/Hospital Authority Hong Kong West Cluster and the trial will be registered in the HKU Clinical trials registry.

Recruitment and screening

Children studying in kindergarten 1 and Nursery 2 will be invited to participate in this proposed study. An invitation letter will be sent to their parents, explaining the objectives and procedures of the study. Only those children whose parents have signed the informed consent will be included in this study. Children will be screened for the following aspects:

1. Plaque assessment using visible plaque index (VPI) (Ainamo & Bay, 1975)
2. Overall tooth status with diagnostic criteria recommended by WHO in 2013, in the form of:

Classification	Description
Decay (d)	presence of dentin carious lesion(s) with or without a restoration.
Missing (m)	the tooth is extracted due to caries.
Filling (f)	presence of a temporary or permanent filling due to caries with no decay.

3. Dental caries status based on ICDAS code score (International Caries Detection and Assessment System Coordinating Committee, 2009; Ismail et al., 2007), which is summarized below:

Code	Classification	Description
0	Smooth & intact tooth surfaces	No evidence of dental caries or questionable changes in translucency of enamel after prolonged drying (around 5 seconds).
1	Visual change in enamel	Color changes due to caries which is not consistent with the clinical appearance of sound enamel, which is seen only after prolonged drying.
2	Distinct visual change	Cariou opacity (white spot lesion) and/or brown carious discoloration which is wider than the natural fissure/fossa that is not consistent with the clinical appearance of sound enamel, when seen wet and after drying.
3	Localized enamel breakdown due to caries with no visible dentin or underlying shadow	The tooth viewed wet might have a clear carious opacity and/or brown carious discoloration which is wider than the natural fissure/fossa that is not consistent with the clinical appearance of sound enamel.

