All tooth surfaces will be first wiped clean and dry by clean gauze and cotton swab for visual inspection of caries. A basic dental charting will be first performed, which the overall primary dentition will be further assessed and recorded based on the presence of decayed (d) missing (m), and filled (f) teeth, as recommended by the WHO in 2013.

Then the ball end of the CPI probes will be used to slide through the pits and fissures of primary molars to detect any enamel cavities or discontinuities. The status of the occlusal surfaces of primary molars will be recorded based on the ICDAS coding system (International Caries Detection and Assessment System Corrdinating Committee, 2009; Ismail et al., 2007).

Children who do not meet all the inclusion criteria will be given an examination report. Parents will be informed regarding the carious teeth and will be advised to seek treatment from private dental practitioners or specialist paediatric dentists promptly. Children with second primary molar(s) that fulfill all the criteria will be included in the study.

The occlusal fissures of each of the upper and lower molars included in the study will be assessed, and the fissure morphology (deep/shallow) and ICDAS score will be recorded.

Randomization and treatment allocation

By using the random numbers generated by stratified block randomization method in a personal computer, children will be randomly allocated to one of the two study groups:

(1) NaF varnish

— Application of a 5% NaF varnish (Duraphat, Colgate-Palmolive Ltd, Waltrop, Germany) on the occlusal surfaces of primary second molars and all other teeth, every 3 months during the study period;

(2) GI sealant

-- Glass ionomer sealant (GC Fuji VII® (pink)) on all primary second molars included in the studies, with no further repair/replacement of the sealant

Interventions

Immediately after the oral examination, a chair-side dental assistant will prepare the materials respective to the groups allocated on the random allocation list.

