A 10% random sample will be re-examined during every examination to monitor intra-examiner reproducibility.

An oral health talk will be given to the parents of the participants. During the talk, the parents will be instructed to choose fluoridated toothpastes and child toothbrushes throughout the period of study. In case of any adverse event during the study, the parents will be advised to contact the principal investigator.

Outcome measures

The primary outcome measure is carious cavity development into dentin (ICDAS code 4, 5 and 6) on the occlusal surfaces of primary second molars over time.

Only one registered dentist will be the examiner in the kindergarten throughout the whole 24-month study period. She will receive training and calibration by epidemiologists before examining the subjects. The following dental equipment will be used:

- (1) Disposable dental mirror attached to a handle with light-emitting diode intra-oral illumination
- (2) World Health Organization CPI periodontal probe(405/WHO probe)

A 10% random sample will be re-examined during every examination to monitor intra-examiner reproducibility. The ICDAS score will be recorded based on the index proposed by Ismail et al., 2007.

Parents will be notified about the development of carious lesions. Advice on oral hygiene maintenance and seeking private dentists for respective dental treatments will be given to the parents in the form of a detailed report.

The proposed study will be a randomized controlled trial with 2 parallel groups. The unit of randomization will be each individual participant, but not each tooth of the mouth.

(iv) Data processing and analysis

Data analysis will be performed using SPSS® Statistics version 23.0 (SPSS Inc, Chicago, IL, USA). All children with missing data resulting from loss to follow-up or unrecorded data will be excluded from the analysis. Data proof-reading will be performed after data entry to identify and correct any errors before analyzing the data. An intention-to-treat analysis will be undertaken. Intra-examiner agreement in the diagnosis of dental caries will be assessed by Cohen's Kappa statistics.

Chi-square test will be used to assess the difference between groups according to the distribution of children's demographic characteristics such as gender, place of birth, oral health-related behavior, use of fluoride toothpaste, snacking habit, parents' education and family income.

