The outcome measures are the mean change in the overall dmft scores and ICDAS code in primary second molars over time. Within-group comparison of changes in mean overall dmft scores and ICDAS scores at 24 months and mean change in overall dmft scores and ICDAS scores will be assessed by applying repeated analysis of variance (ANOVA) (or Friedman test for non-parametric data).

Student's t-test will be applied to differentiate the comparability between the treatment groups according to the subject's baseline conditions, including the child's age, dmft score and VPI score.

Since more than one molar will be included from one child, GLIMMIX procedure will be used to adjust for the clustering effect. The first level and second level will be the primary second molar and the subject

respectively. This analysis accounts for the correlation (clustering) between observations of multiple molars from the same child.

A multi-level logistic regression analysis will be performed to analyze the effects of independent variables on the ICDAS scores at the 6, 12, 18 and 24 month examinations. The independent variables included the child's demographic characteristics, oral health-related behaviors and clinical characteristics (gender, place of birth, frequency of tooth brushing, use of fluoride toothpaste, snacking habits, mother's education, father's education, family income, VPI score, dmft score and the treatment group). The level of statistical significance for all tests will be set 5%.

Key References:

3. American Academy of Pediatric Dentistry. Guideline on caries-risk assessment and management for infants, children, and adolescents. *Pediatr Dent.* 2013;35(5): E157-64.
4. American Dental Association Council on Scientific Affairs. Professionally applied topical fluoride: evidence-based clinical recommendations. *J Am Dent Assoc.* 2006;137(8): 1151-9.

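### The multi-level logistic model omits each molar's baseline ICDAS code, which is already recorded and is the starting value of the primary outcome; prespecify it as a covariate

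*Combined protocol and SAP*

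**What the plan says.** Section d)(iv) plans a multi-level logistic regression "to analyze the effects of independent variables on the ICDAS scores at the 6, 12, 18 and 24 month examinations". Its covariates are the child's demographics, oral health behaviours, parental education and clinical scores, ending with "family income, VPI score, dmft score and the treatment group". All describe the child. None describes the molar, although the same section makes the molar the first level of the clustered analysis.

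No other analysis supplies the adjustment. The sentence that the "GLIMMIX procedure will be used to adjust for the clustering effect" names no covariates. The ANOVA or Friedman analysis is described as within-group. The baseline t-tests cover age, dmft and VPI.

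The primary outcome (Outcome measures) is "carious cavity development into dentin (ICDAS code 4, 5 and 6) on the occlusal surfaces of primary second molars over time". Exclusion 5 in section d)(i) removes second molars "with caries in dentin indicated by ICDAS code 4, 5 or 6", so a molar at code 0, 1, 2 or 3 can enter. Under Tooth status in the clinical examination, for each included molar "the fissure morphology (deep/shallow) and ICDAS score will be recorded" before treatment.

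**The concern.** The omitted covariate is the starting value of the outcome scale. If a molar at code 2 or 3 is more likely to reach dentin than one at code 0, three things follow.

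- A logistic model without the code estimates a treatment log odds ratio pulled toward zero, so power is lost.
- A chance excess of early-lesion molars in one arm shifts the estimated odds ratio, and nothing in the model corrects it.
- Adjustment decided only after an imbalance has been seen would be post hoc.

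The list also does not say that VPI and dmft are baseline values, although both are re-recorded at follow-up. Follow-up dmft can count the outcome molars themselves.

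The model is presented as exploring independent variables, not as the primary treatment comparison. It is nevertheless the only planned model that names both treatment group and covariates.

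**Working it through.** **1. Inputs from the documents.** The plan requires 102 children per group at 5% significance and 90% power. Its inflation step reproduces: 102 × 1.25 = 127.5, rounded up to 128. The 102 itself cannot be reproduced because no arm-specific rates are given, so it is taken as stated.

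**2. Can baseline dmft stand in?** Decay (*d*) means "presence of dentin carious lesion(s) with or without a restoration", and molars with fillings are excluded. An included molar with no dentin lesion therefore adds 0 to dmft whether it is at code 0 or code 3. Exclusion 1 also removes "Children with the presence of caries of ICDAS code 3, 4, 5, or 6 on other primary teeth". If that means teeth other than second molars, baseline *d* can come only from second molars that exclusion 5 takes out. Missing or filled teeth can still raise dmft, but that is child history and does not separate one included molar from another.

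**3. Power with and without the code.** All settings below are assumptions.

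- 102 children per arm, 4 molars each (2 × 102 × 4 = 816 molars), true odds ratio 0.5, 2,500 runs per setting.
- Random-intercept logistic model, maximum likelihood with 15-point Gauss-Hermite quadrature, Wald test, child SD 1.0, latent within-child correlation of baseline code 0.5.
- Planned model: treatment, baseline dmft and one VPI-like child predictor. Each predictor loads 0.4 on the child's caries activity and 0.4 on the child effect. The other listed covariates are not simulated.
- Amended model: the same plus code (0, 1–2, 3), with code 3 merged into 1–2 if it has fewer than 20 molars.
- Lesion mix at codes 0 / 1–2 / 3: few = 75/22/3%, more = 50/35/15%.
- Varnish-arm risk at those codes for the median child: none 20/20/20%, weak 15/20/30%, moderate 8/25/55%, strong 5/25/65%.

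| Lesions | Prediction | Planned | Amended | Change (points) |
|---|---|---|---|---|
| Few | none | 84.4% | 85.0% | +0.6 |
| Few | weak | 81.0% | 81.2% | +0.2 |
| Few | moderate | 71.4% | 73.0% | +1.6 |
| Few | strong | 61.7% | 66.4% | +4.7 |
| More | weak | 83.2% | 82.5% | -0.7 |
| More | moderate | 77.7% | 81.0% | +3.3 |
| More | strong | 70.1% | 77.5% | +7.4 |

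The Monte Carlo SE of each change is 0.2 to 0.8 point. Rejection under the null is 5.2–5.9% (planned) and 5.4–6.0% (amended).

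**4. Where the gain comes from.** The true log odds ratio is -0.693. Approximate power is Φ(|estimate|/SE − 1.96).

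- Few, strong, planned: 0.627/0.281 = 2.23, Φ(0.27) = 0.61. Amended: 0.703/0.299 = 2.35, Φ(0.39) = 0.65.
- More, strong, planned: 0.590/0.238 = 2.48, Φ(0.52) = 0.70. Amended: 0.700/0.258 = 2.71, Φ(0.75) = 0.77.

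The SE rises slightly. The gain comes from removing the attenuation, and the approximation agrees with the simulated power.

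**5. Sensitivity, few lesions.** With 20% of codes misclassified: moderate 71.4 to 72.5%, strong 61.7 to 65.7%. With child SD 2.0: moderate 48.7 to 47.5%, strong 44.6 to 45.2%.

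**6. Chance imbalance under a true null.** Without stratification on caries, the SD of the between-arm difference in the share of molars at codes 1–3 is 4.2 points (few) or 4.9 points (more). At a 1-SD excess the planned odds ratio is 1.04 and 1.07 (few; moderate, strong) and 1.06 and 1.09 (more; moderate, strong). With the code included it is 0.98 to 0.99. With no or weak prediction the planned value is 0.98 to 1.01.

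**7. Other estimators and settings.** Logistic regression with child-clustered standard errors (2,000 runs) gives 71.8 to 72.9% (few, moderate), 62.8 to 66.8% (few, strong) and 78.8 to 82.5% (more, moderate). A more favourable setting has 10% of molars at code 3, three molars per child and treatment as the only other term. It gives gains of 1–3, 6–10 and 15–17 points for log-odds slopes per code of 0.5, 1.0 and 1.5. The smaller figures in step 3 are relied on here.

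**8. If follow-up dmft were used.** In the clustered-SE runs, with assumed new decay on other teeth, replacing baseline by follow-up dmft cut power from 71.8 to 49.8% (few, moderate) and from 78.8 to 52.3% (more, moderate). The median odds ratio moved from 0.54 to 0.65 and from 0.56 to 0.69.

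**The case against.** The strongest reply is that the benefit is small and uncertain. That stands in large part. Two simulated settings lose power, the weak-prediction changes are indistinguishable from zero, and a nominal +0.6 appears even when the code predicts nothing. The Introduction says both that incipient lesions may progress and that remineralization works on them, so the strength of prediction is unknown. The moderate, few-lesions gain of 1.6 points is at least two Monte Carlo SEs, and the other estimator also shows a gain (1.1 points), but it is small.

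The imbalance effect is also small next to sampling error. Log odds ratio shifts of 0.04 to 0.09 against SEs of 0.24 to 0.30 are roughly 0.14 to 0.36 of one SE. The unnamed randomisation strata might include caries status, which would reduce it further.

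On dmft, a dentin lesion on a non-occlusal surface of an included molar might count as *d*, and the risk-based inclusion list, which admits children with visible cavities or fillings, sits awkwardly with exclusion 1. These are edge cases. They do not let dmft distinguish an included molar at code 0 from one at code 3.

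Finally, the simulated model carries two child covariates instead of the full list and has no repeated visits, and the plan does not call this model primary. Both are true. The second is why the fix begins by naming the between-group model.

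**Conclusion.** The point holds as a low-cost improvement, not a validity error. The molar's baseline code is collected, lies on the outcome scale and appears in no planned between-group model. Under the assumptions above, including it changes power by about -1 to +7 points. The gain is about 2 to 5 points with few early lesions, a moderately to strongly prognostic code and child SD 1.0. It vanishes if the code predicts little or if differences between children dominate. Inclusion also removes most of the shift in the odds ratio from a chance imbalance in early lesions. Leaving the timing of dmft and VPI open carries a larger potential loss, but only if follow-up values are actually used.

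**What to change.** Amend section d)(iv) to do the following.

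- State which multilevel model is the between-group comparison of ICDAS 4–6.
- In that model, prespecify each molar's baseline ICDAS code as a molar-level covariate beside treatment group.
- Give a rule for sparse levels, for example merging code 3 with codes 1–2 if it has fewer than 20 molars. At 3% of 816 molars about 24 are expected, so the rule may be needed.
- State that VPI and dmft enter as baseline values only.
- Include the randomisation strata once they are named.

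Fissure morphology, also recorded at baseline, may be added, but its prognostic value within second molars is an assumption.

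The cost is SAP wording only. No extra data or children are needed, but the merging rule must be written and the strata named first.

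### Baseline dmft, the only caries covariate, is likely to be mostly zero after exclusion 1; add the enamel-lesion (ICDAS) data already charted at baseline beside it

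*Combined protocol and SAP*

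**What the plan says.** Section d)(iv) lists the independent variables of the multi-level logistic regression for ICDAS at 6, 12, 18 and 24 months. The list ends with "VPI score, dmft score and the treatment group" and contains no other caries measure. The same section compares the arms at baseline by t-test on three variables, "including the child's age, dmft score and VPI score". It does not say which visit's dmft enters the model, and Follow-up evaluation records dmft again at every examination.

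Four other places determine what baseline dmft can contain:

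- Section d)(i), exclusion 1: "Children with the presence of caries of ICDAS code 3, 4, 5, or 6 on other primary teeth".
- Section d)(i), exclusion 5: "Second primary molars that are (i) with caries in dentin indicated by ICDAS code 4, 5 or 6", and also those "with fillings and/or sealants".
- Recruitment and screening defines d as "presence of dentin carious lesion(s) with or without a restoration". Separate components count teeth extracted for caries (m) and teeth filled without decay (f).
- Tooth status, on entry: "Children with second primary molar(s) that fulfill all the criteria will be included in the study".

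Tooth status also describes what is charted before treatment: "The status of the occlusal surfaces of primary molars will be recorded based on the ICDAS coding system". Fissure depth and ICDAS code are recorded for each study molar as well. None of these is in the covariate list.

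**The concern.** A baseline covariate earns its place by separating children at different risk of the outcome. dmft does this well in an unselected preschool population, but this trial selects on it. Exclusion 1 removes active dentin decay from the teeth other than the second molars, and d does not see enamel lesions. What still varies on those teeth is ICDAS 0 to 2, which dmft cannot register.

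Two things follow. The model's caries term may explain less of the between-child variation than its place in the list suggests, so available precision is not used. And a t-test on a mostly zero count can look balanced while the arms differ by chance in current caries activity, so the baseline table gives less reassurance than it appears to.

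**Working it through.** The plan gives no figure for baseline dmft in the enrolled sample, so there is nothing to reproduce. The check has three parts.

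**1. Which components survive the exclusions.** Exclusion 1 is read here as applying to the 20 − 4 = 16 teeth that are not second molars.

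| Component | Study second molars | Second molars left out of the study | Other 16 teeth |
|---|---|---|---|
| d (dentin) | 0, by exclusion 5 | can occur | 0, by exclusion 1 |
| m | not applicable | can occur | not excluded |
| f | 0, by exclusion 5 | can occur | not excluded |
| ICDAS 1–2 | not counted in dmft | not counted | not counted |

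Exclusion 5 removes teeth, and a child enters with one eligible second molar, so up to 4 − 1 = 3 affected second molars can still count. On the other 16 teeth only m and f remain. The Introduction puts mean dmft at 2.5 (2011) and untreated decay above 90%. Treating that as a share of all dmft teeth, m + f averages at most about (1 − 0.90) × 2.5 = 0.25 teeth per child in the source population.

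**2. How often dmft would be zero (illustrative).** Each simulated child had a per-tooth caries probability drawn from a beta distribution. It was fitted to mean dmft 2.5 with 49% caries-free, or, for younger children, mean 1.5 with 65% caries-free. Ten per cent of carious teeth were treated, either spread over teeth or clustered in children. The odds of caries in second molars were 1, 3 or 6 times those of other teeth. Only the mean of 2.5, the caries prevalence above 50% and the untreated share come from the Introduction; the rest is assumed.

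| Reading of exclusion 5 | dmft = 0 | Mean dmft |
|---|---|---|
| As worded (removes teeth) | 75–95% | 0.06–0.59 |
| Stricter (active dentin caries on any second molar removes the child) | 90–98% | 0.02–0.43 |

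Under the text as worded, 1–12% of children had dmft of 2 or more. In every scenario only about 1–9% had any dmft on the 16 other teeth. The 75% comes from the sixfold-odds setting, where the simulated population mean rises to 3.21, above the 2.5 in the Introduction.

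**3. What an enamel-lesion term might be worth.** All inputs here are assumptions except the 102 children per arm:

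- 1–4 molars per child and a child random-effect SD of 1.5
- molar incidence of 8% or 15% and a true odds ratio of 0.45
- dmft above zero in 10% of children
- a random-intercept logistic model with a likelihood-ratio test, 600 simulated trials per setting

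| Share of between-child risk explained by first-molar count | Power without → with, 8% incidence | Power without → with, 15% incidence |
|---|---|---|
| 10% | 47% → 47% | 61% → 62% |
| 20% | 47% → 50% | 60% → 65% |
| 30% | 44% → 50% | 57% → 64% |

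The gain is 0–1, 3–5 or 6–7 points. The Monte Carlo standard error of each power figure is about √(0.5 × 0.5 / 600) = 2 points.

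For chance imbalance, the slope of the estimated log odds ratio on the imbalance is 0.36–0.94 per SD without the term. An imbalance of 0.2 SD then shifts it by 0.2 × 0.36 = 0.07 to 0.2 × 0.94 = 0.19, a factor of e^0.07 = 1.07 to e^0.19 = 1.21 in the odds ratio. With the term the slope is at most 0.19 in size, so the shift is at most 0.2 × 0.19 ≈ 0.04.

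The SD of such an imbalance is about √(2/102) = 0.14 (0.15 in the simulation). An imbalance of 0.2 SD or more in either direction would thus occur in roughly 15–18% of trials.

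To put the shift in proportion, ln 0.45 = −0.80. Power of 47% implies a standard error near 0.80 / (1.96 − 0.08) = 0.42, and 61% implies 0.80 / (1.96 + 0.28) = 0.36. The shift is then about 0.07/0.42 = 0.2 to 0.19/0.36 = 0.5 of a standard error.

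**The case against.** A reader might infer that exclusions 1 and 5 together force dmft to about zero in almost every enrolled child, so that the model does not adjust for caries experience at all. The documents do not support that. Exclusion 5 drops teeth, not children. Nothing excludes extracted teeth, or filled teeth other than second molars. The inclusion table itself lists decayed, missing or filled surfaces and visible cavities or fillings as qualifying risk factors. With the text as worded, about 5–25% of children could have dmft above zero. A decayed second molar outside the study is caries experience on the same type of tooth as the outcome, so dmft keeps some value and should not be discarded.

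A reader might also infer bias. Randomisation leaves the comparison valid, and the standard error already allows for chance imbalance.

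Three further points stand:

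- Nothing in the documents shows that first-molar enamel lesions predict dentin caries on second molars. The study molar's own baseline code (0 to 3 is admissible) is the more direct candidate, and the planned analysis of change in ICDAS already uses it implicitly.
- The stated assumptions of the power calculation do not mention plaque, snacking, brushing or income, which the plan already adjusts for. If these share risk with enamel lesions, the gain is smaller.
- The phrase for other primary teeth in exclusion 1 is undefined, and how much dmft survives depends on it.

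The unstated time point does not rescue the term. A follow-up dmft would vary more, but it is measured after randomisation and can contain the outcome itself.

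**Conclusion.** The point holds as a minor, inexpensive improvement. Baseline dmft is likely to be mostly zero, to reflect mainly ineligible second molars and past treatment, and to carry little information about current caries activity on the other teeth. It is nevertheless the plan's only caries covariate and the only caries measure in its baseline t-tests, while more informative baseline data are collected and not used as covariates.

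The loss is in precision and in protection against chance imbalance: about 0 to 7 power points, and a conditional shift of about 0.2–0.5 of a standard error at an imbalance of 0.2 SD. These sizes rest on assumed incidence, clustering, effect and predictive strength. If the enamel count explains only 10% of between-child risk, the gain is effectively nil. That dmft omits enamel lesions, and that exclusion 1 removes active dentin decay on the other teeth, follows from the plan's own definitions.

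**What to change.** In section d)(iv):

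1. State that dmft in the logistic model is the baseline value, and keep it.
2. Add beside it the number of first primary molars with ICDAS 1–2 at baseline, from the Tooth status record. Consider the study molar's own baseline ICDAS code as well, as an equally available and more direct term. Fix the choice before outcome data are seen.
3. Report the first-molar count by arm in the baseline table alongside dmft.

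In section d)(i), define which teeth exclusion 1 covers, and reconcile it with the inclusion criteria on cavities, fillings and affected surfaces, since the content of dmft depends on that reading.

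The cost is a few sentences and one model degree of freedom, or two if the study molar's code is entered as a single score. No new data are needed, because the codes are recorded before treatment.
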